### **5.1. Safety Assessments**

The investigational device carries the same risk as obtaining an adult ECG, hence qualifying for the IDE 21 CFR Part 812.3(k) non-invasive. We anticipate that no serious adverse events will occur due to monitoring. It is possible that some subjects may experience slight skin irritation from the gel associated with the sensors; however, these reactions are not severe, are self-limited, and resolve without specific treatment.

For subjects experiencing internal monitoring, there is added medical risk to the subject. If internal monitoring is clinically indicated, the risk to those subjects is not attributable to the study.

All subjects undergoing internal monitoring will have clinical indications for the procedure. Subjects will not undergo internal monitoring expressly for purposes of this study, and the risk of internal monitoring is not attributable to the study.

### **5.2. Costs to the Subject**

There will be no cost to the patient or the patient's insurance as a result of study enrollment. The electrodes, EMG, and computer are being provided by the study Sponsor.

### **5.3. Payment for Participation**

There is a small stipend (\$50) given to subjects to defray the time-cost, potential discomfort, and slight risk for participation. Subjects who initiate the study but who are unable to complete a full 60 minute session will be compensated the full amount if any recording has already been initiated.

#### **Compensation to Subjects**

Subjects who complete a 60 minute study will receive \$50 compensation in the form of a gift card, to defray the cost of additional monitoring time and inconvenience of simultaneously monitoring with EMG/ECG.

## **6. Return of Individual Research Results**

Research results will not be directly provided to the subjects. See safety (above) regarding the incidental finding of non-reassuring fetal heart rate patterns.

## **7. CONCOMITANT AND DISALLOWED MEDICATIONS**

There are no required treatments or disallowed medications.

## **8. SUBJECT WITHDRAWALS**

Subjects will be advised in the written informed consent that they have the right to withdraw from the study at any time without prejudice. Subjects may be withdrawn by the investigator if the clinical circumstances require immediate delivery (e.g. non-reassuring fetal heart rate, abruption, etc.). If a subject requires withdrawal by the study investigator, uEMG recording will be stopped at that time and no further data will be collected.

## **9. STUDY DEVICE**

### **9.1. Study Device**

The study will utilize body surface electrodes, an 8-channel EMG, and computer. The system being used is the PreTel Regional Contraction uEMG/ECG Fetal Monitor. This device was reviewed by URMC Engineering Department for RSRB#59426 and was approved for external use in the study design. The PreTel Monitor is manufactured by Cooper Consulting Services to

meet electromagnetic compliance (EMC) and safety IEC 60601-1 for medical devices, development and process documentation ISO 14971 (hardware) and IEC 62304 (software).

Each physiological amplifier will be tested for equivalence to the Porti Physiological Amplifier which has been cleared by the FDA for use as per #K063599 for the intended use by or under the direction of a physician for the acquisition of EMG/ECG signals. All of the study equipment will be supplied by the study investigator, [name], at PreTel, Inc. and will be returned upon completion of enrollment.

All PreTel sensors (pads) utilized in this protocol have been manufactured to the requirement of this document, and more specifically in accordance with ISO 13485:2003, section 7.5 and with the Food, Drug, and Cosmetic Act Good Manufacturing Practices regulation and the Code of Federal Regulations (CFR) Title 21 Part 820 (and part 211 where applicable). All EMG sensors to be utilized in this study have been manufactured as per the above requirements by Katecho (Des Moines, IA). Additionally, commercially available ECG pads, such as those supplied by AMBU Corporation, will be used as the reference and fetal ECG sensors.

The device will be stored in the locked storage cabinet in the Ultrasound Suit for labor and delivery at Strong Memorial Hospital. Only study personnel will have access to the device.

#### **9.2. Accountability of Investigational Supplies**

The principal investigator at the University of Rochester, [name], will be responsible for receipt, storage, dispensing, collection, accountability and disposal of the investigational supplies as applicable.

### **10. SAFETY AND REPORTABLE EVENTS**

The investigational device carries the same risk as obtaining an adult ECG, hence qualifies for the IDE 21 CFR Part 812.3(k) non-invasive. We anticipate that no serious adverse events will occur due to monitoring. It is possible that some subjects may experience a slight skin irritation due to the gel associated with the sensors; however, these reactions are not severe, are self-limited, and resolve without specific treatment.

For subjects experiencing internal monitoring, there is added medical risk to the subject. If internal monitoring is clinically indicated, the risk to those subjects is not attributable to the study.

All subjects undergoing internal monitoring will have clinical indications for the procedure. Subjects will not undergo internal monitoring expressly for purposes of this study, and the risk of internal monitoring is not attributable to the study.

#### **10.1. Responsibilities for Reporting Serious Adverse Events**

The Principle Investigator will record all serious adverse experiences that occur during the study period in an adverse event log. The study period for reporting serious adverse events (e.g., from the time of signing consent to final study visit) will be indicated, as will the personnel who needs to be notified and the time frame for notification. The Principle Investigator will comply with regulations and RSRB policy regarding the reporting of adverse events.

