### 3. CHARACTERISTICS OF THE RESEARCH POPULATION

#### 3.1. Subject Characteristics

##### a) Number of Subjects:

We plan to recruit up to 50 study subjects to complete the entire 60 minutes of testing and consent to have their chart reviewed after delivery to collect all objective outcome data as outlined in our study plan. Data from those who start the uEMG recordings but are unable to complete the full duration will still be analyzed so long as the reason for their withdrawal is not secondary to their withdrawal of consent. Those who withdraw consent will be excluded for data collection and analysis.

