**b) Exclusion Criteria:**

- Twins, triplets and larger number multifetal gestations
- Age less than 18 years
- Humans without a uterus
- Non-English reading and/or speaking
- Significant uterine anomalies such as didelphys or bicornuate uterus (women with small, clinically insignificant anomalies such as uterine fibroids are not excluded).
- Participants cannot be participating in any other research study or protocol regarding uterine contraction monitoring during the same study period as required for our study.
- Known allergy to ECG pad adhesive
- Non-living fetus
- Major fetal malformation
- Fetal distress, or other indications for emergent delivery

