For both the preterm or term subjects who present to triage, there is the possibility that they may not ultimately progress in labor. These subjects are also eligible for an EMG study session for 60 minutes while their labor status is being evaluated. If they are deemed to not be in labor (i.e. no cervical change) and are discharged (or admitted for extended monitoring, as may occur in the preterm setting or at term for “therapeutic rest”), they will not be excluded from analysis, and they will be allowed to participate in another session either when they begin laboring (i.e. if admitted) or if they are discharged and then return to Triage for another labor evaluation. Recordings may be stopped and restarted multiple times for a single subject if needed.

During the 60+ minutes of EMG pad placement, subjects must also have standard tocometry monitoring and fetal heart rate monitoring. The standard monitoring can consist of either external tocodynamometry (Toco) or an intra-uterine pressure catheter (IUPC) and either external Doppler monitoring of the fetal heart rate or a fetal scalp electrode (FSE). Which type of monitoring is used will be at the discretion of her regular obstetric care team and will not be altered by participating in the study (i.e., the study will not require the patient to have internal monitoring IUPC/FSE). Participation during the 60 minutes of recording does however require some form of continuous monitoring, and therefore subjects desiring intermittent fetal heart rate auscultation or intermittent palpation for contractions, will not be eligible for participation unless they are willing to have standard monitoring for the duration of the study period. Clinical decisions will only be made based on standard uterine and fetal monitoring and examinations.

Uterine EMG recordings, along with the fetal monitoring paper record, will be sent to PreTel. Assessment of the recordings for uterine contractility and fetal heart rate will then be performed by those investigators trained in the analysis ([name]). The EMG data will be compared to the tocometry data to determine correlation or “R” value.

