### 11.2. Protection Against Risks

If a participant has any irritation from the uEMG pads, they may ask for their removal and withdraw from study participation.

Protection against a breach of confidentiality: A note regarding their consent to participation in the study will be placed in their medical record in the Provider “Sticky Note” to inform hospital staff that the subject is in the study. This will be done only if the subject would like to participate in the study beyond the first uterine EMG recording session. If subjects are only participating in a single uEMG monitoring session, then no information will be recorded in their medical record. The “Sticky note” is not a part of the patient’s permanent medical record and is removed after the pregnancy episode is complete (which occurs following delivery). The information in the sticky note will state: “subject enrolled in UEMG Study”. No other identifying information will be recorded in the medical record. This note is necessary to ensure that study personnel are notified when the patient presents to triage at future dates/times to determine if the subject would like to proceed with additional uterine EMG monitoring per the protocol. The risk of a confidentiality breech will also be mitigated, by using only a unique ID code on all documentation. Without the ID code key, it will be impossible to link the subjects’ participation information to their confidential information. Only URMC study investigators will have access to the key code. Information sent to the study sponsor for data analysis will have no individual identifying information.

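### The only adverse event log specified is for serious events, so the one physical device risk the protocol names, non-serious skin irritation, has no specified count

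*Combined protocol and SAP*

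**What the plan says.** Section 10.1 sets the recording rule: "The Principle Investigator will record all serious adverse experiences that occur during the study period in an adverse event log". It adds a general commitment: "The Principle Investigator will comply with regulations and RSRB policy regarding the reporting of adverse events".

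Section 5.1 names the expected device effect: "It is possible that some subjects may experience slight skin irritation from the gel associated with the sensors". Section 10 repeats it almost word for word. Both describe such reactions as mild and as clearing up untreated. Section 11.1 calls the risk theoretical and equates it with that of ordinary EKG pads. The other risk it names is a breach of confidentiality, which is not a device effect.

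Section 11.2 gives the response to irritation: "If a participant has any irritation from the uEMG pads, they may ask for their removal and withdraw from study participation". Section 2.1 separately lets a woman have the pads taken off on request at any point. Section 3.1 a) keeps data from women who start but cannot finish a recording, unless the reason is withdrawal of consent, and then says: "Those who withdraw consent will be excluded for data collection and analysis".

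Section 2.1 lists 11 CRF items, introduced as coming from the medical record. None is a skin reaction or an adverse event. The endpoints set out under Sections 14.2 and 14.3 cover heart rate and contractions only.

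For women found not to be in labor, Section 5 permits repeat sessions: "they will be allowed to participate in another session either when they begin laboring". The related exclusion in Section 3.2 b) is "Known allergy to ECG pad adhesive".

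**The concern.** Section 1.1 describes a feasibility study meant to characterize the device clinically. Section 1.2 describes a sensor with a new shape, an open 6 cm by 6 cm hexagon, and Section 2.1 allows up to 15 electrode pads plus a ground. Skin irritation is the one physical effect of these pads that the protocol expects. A log restricted to serious events excludes that effect by the protocol's own description of it.

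Two things are at stake. First, an empty log at the end of the study would carry no information about irritation, yet it could be read as supporting the Section 11.1 comparison with ordinary EKG pads. Second, if stopping because of irritation is handled as withdrawal of consent, the affected women leave the dataset. Their contraction and heart-rate recordings would be lost along with any skin observation. Neither can be recovered after the study.

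**Working it through.** **Step 1. Could irritation enter the data by a specified route?**

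- Adverse event log (Section 10.1): serious events only. Irritation as described in Sections 5.1 and 10 does not qualify.
- CRF items (Section 2.1): 11 listed, none on skin or adverse events. Appendix 2 is not in the supplied text, so the form itself cannot be checked.
- Medical record: Section 13 keeps research data out of it, so later chart review is not a dependable route.
- Endpoints (Sections 14.2 and 14.3): none on skin reaction or tolerability.
- General channels: Section 10.1 defers to regulations and review-board policy, and Section 14.3 sends safety concerns to the local investigators and then the sponsor. Neither says how, or on what form, a non-serious event is recorded.

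No specified step produces a count.

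**Step 2. What happens to the data of a woman who stops because of irritation?**

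- Under Section 2.1 the pads come off on request, and under Section 3.1 a) her data are kept.
- Under Section 11.2 she may have the pads removed and withdraw from participation. If that is read as withdrawal of consent, Section 3.1 a) excludes her.

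The protocol does not say which reading applies. The same event can lead to data kept or data lost.

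**Step 3. What would a recorded count give?** The plan states no figure here, so there is none to reproduce. The inputs are n = 50 (maximum recruitment) and n = 23 (calculated sample size), both from Section 14.1.

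With 0 cases in n women, the exact one-sided 95% upper limit is 1 − 0.05^(1/n):

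- n = 50: 1 − 0.05^(1/50) = 0.058, or 5.8%
- n = 23: 1 − 0.05^(1/23) = 0.122, or 12.2%

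Exact (Clopper-Pearson) two-sided 95% intervals for n = 50:

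- 2 cases (4%): 0.5% to 13.7%
- 5 cases (10%): 3.3% to 21.8%

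The documents give no irritation rate. Taking 1% to 10% as an assumption, the chance of at least one case among 50 women is 1 − (1 − p)^50:

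| Assumed rate p | Expected cases (50p) | Chance of at least one |
|---|---|---|
| 1% | 0.5 | 39% |
| 2% | 1.0 | 64% |
| 5% | 2.5 | 92% |
| 10% | 5.0 | 99% |

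These figures show what a skin check in every woman would yield. Without one, zero logged events is compatible with any rate.

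**The case against.** The strongest reply is that this is a minimal-risk study. The sensors use the same material as standard ECG pads (Section 1.2), no endpoint estimates irritation, and the plan nowhere promises an irritation rate. Appendix 2 may already contain a skin item. The Section 2.1 list is introduced as chart information, so a bedside observation need not appear there. The general channels in Sections 10.1 and 14.3 are not limited to serious events. All of this stands, and it keeps the point modest. It does not supply a recording step, and the Section 11.1 comparison remains one that the study could inform but, as specified, will not.

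A reader might infer three stronger things that the documents do not support:

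- *Women with irritation are made to withdraw and are then excluded.* Section 11.2 is permissive, Section 2.1 allows pad removal alone, and Section 3.1 a) keeps early stops that are not withdrawals of consent.
- *Irritation is never recorded.* With Appendix 2 and the review-board policy unseen, one can say only that no recording step is specified.
- *Women who reacted are re-exposed without anyone being able to know.* A woman who has withdrawn has no further session, and one who returns knows that she reacted. What is missing is a record that staff can consult. The Section 3.2 b) exclusion concerns adhesive allergy, whereas the irritant named in Sections 5.1 and 10 is gel, so the two should not be merged.

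Nor does the mention of a final study visit in Section 10.1 show a defective reporting window. It is given only as an example, in a sentence saying the period will be indicated.

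**Conclusion.** The concern holds in a limited form. The only log specified is for serious events, the only named physical device risk is non-serious, and no listed CRF item or endpoint captures it. The study has no specified numerator for pad irritation, so an absence of logged events could not support the Section 11.1 statement. Sections 2.1, 3.1 a) and 11.2 also need to be reconciled on the data of a woman who stops because of irritation.

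In size, a skin check in all 50 women would turn no information into an upper limit of 5.8% if no case occurred (12.2% if only 23 were checked). This assumes that every woman is checked and counted once. The conclusion does not depend on the assumed 1% to 10% rates. It does depend on Appendix 2 containing no skin item; if it has one, the recording gap narrows to the log and the handling of withdrawal. The primary contraction and heart-rate analyses are affected only through any data lost by the ambiguity over withdrawal.

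**What to change.** 1. Extend the Section 10.1 log to all device-related events, serious or not.
2. Add a short CRF item at each pad removal: skin reaction (none, mild, moderate, severe) and pads removed early for irritation (yes/no). Make it available to staff before any repeat session under Section 5. Who may continue monitoring is a clinical matter and is not proposed here.
3. Reconcile Sections 2.1, 3.1 a) and 11.2 so that pad removal for irritation is recorded separately from withdrawal of consent, with the handling of data stated for each.
4. Report the per-woman irritation rate with an exact confidence interval, counting a woman once if she reacted in any session.

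The cost is a few CRF lines, one protocol paragraph and about a minute per session at pad removal. The downside for the sponsor is that the study may report a non-zero irritation rate.

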## 11. RISK/BENEFIT ASSESSMENT

### 11.1. Potential Risks

All monitoring is passive in nature and is done in concert with standard monitoring. Therefore there is no risk of applying the additional EMG pads. As noted in section 9, there is a theoretical risk of irritation from the gel on the pads, which is no different from the pads used for standard EKG recordings.

A breach of confidentiality is a risk of participation, as the medical record will need to be reviewed to gather the necessary clinical information.

### 11.2. Protection Against Risks

If a participant has any irritation from the uEMG pads, they may ask for their removal and withdraw from study participation.

Protection against a breach of confidentiality: A note regarding their consent to participation in the study will be placed in their medical record in the Provider “Sticky Note” to inform hospital staff that the subject is in the study. This will be done only if the subject would like to participate in the study beyond the first uterine EMG recording session. If subjects are only participating in a single uEMG monitoring session, then no information will be recorded in their medical record. The “Sticky note” is not a part of the patient’s permanent medical record and is removed after the pregnancy episode is complete (which occurs following delivery). The information in the sticky note will state: “subject enrolled in UEMG Study”. No other identifying information will be recorded in the medical record. This note is necessary to ensure that study personnel are notified when the patient presents to triage at future dates/times to determine if the subject would like to proceed with additional uterine EMG monitoring per the protocol. The risk of a confidentiality breech will also be mitigated, by using only a unique ID code on all documentation. Without the ID code key, it will be impossible to link the subjects’ participation information to their confidential information. Only URMC study investigators will have access to the key code. Information sent to the study sponsor for data analysis will have no individual identifying information.

### 11.3. Potential Benefits to Subjects

There are no other potential benefits to the subjects

### 11.4. Alternatives to Participation

None

## 12. CONFIDENTIALITY OF DATA AND INFORMATION STORAGE

Participants’ consent forms will be kept in a secure locked filing cabinet in [name]’s locked office.

Patients’ names and medical record numbers will be linked to a code by date as follows: mm/dd/yy-xx, where mm/dd/yy is the date of study, and xx refers to subject #01 through 50. A master key will be maintained on a password-protected spreadsheet on the secure OB/GYN I-Drive at URMC.

The CRF's will be kept in a locked file in the office of [name].

Uterine EMG recordings will be labeled with the participants' unique identifier codes and not with their names, MRNs or birthdates.

Access to the I-Drive Key will be available only to those personnel responsible for consenting participants. Once all data is collected and EMG recordings have been completed this EMG data will be sent to the PreTel, Inc. electronically via e-mail, as there is no identifying patient information recorded on these. The data sheet is also de-identified, with only the unique identifier listed; this data sheet will also be sent to PreTel, Inc., (a.k.a. [name]) via URMC email. The Key spreadsheet will remain at URMC in the password protected file on the encrypted I-Drive. Following completed enrollment the password to the Key sheet will be changed so that only the PI's have access to this key and study coordinators will no longer have access.

### **13. RESEARCH INFORMATION IN MEDICAL RECORDS**

No research data will be included in the participants' medical records.

### **14. DATA ANALYSIS AND MONITORING**

#### **14.1. Sample Size Determination**

This project is a pilot study to assess the reliability of uEMG compared to tocodynamometry for recording uterine contractions. Patient-to-patient variations include body habitus, uterine size, contraction strength and the amount of cervical dilation. We are not capable of controlling for all clinical variables, but assume that term patients carrying one baby in active labor will have contractions that are nearly uniform in producing uterine EMG signals. Thus, for these analyses, we assume that there are no subcategories of patient variables in the study population.

A sample size of 23 was determined using Odds Ratio statistics, assuming a 50% discrimination is clinically the minimum acceptable,  $\alpha=0.05$ ;  $\beta=0.8$ ; expected .75/.25 ratios. For each patient of 60 minutes of recording, we anticipate a minimum of 10 contractions could be observed. On average, we assume 10 contractions, for 23 patients, or 230 contractions.

However, to accommodate for patients who are enrolled in the study but who are subsequently excluded because of inability to complete the monitoring session, we will plan to recruit up to 50 patients.

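### Section 14.1 prints beta = 0.8, which cannot give the stated 23 and leaves the test and its sidedness unstated; sections 2.1, 3.1 and 14.1 disagree on recordings started but not finished

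*Combined protocol and SAP*

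**What the plan says.** **Sample size.** Section 14.1 calls the project a pilot and gives this basis: "A sample size of 23 was determined using Odds Ratio statistics, assuming a 50% discrimination is clinically the minimum acceptable", with alpha 0.05, beta 0.8 and "expected .75/.25 ratios". It gives no formula, number of groups, sidedness or power. It assumes 10 contractions per patient, hence 230 from 23 patients.

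**From 23 to 50.** Section 14.1 raises recruitment to as many as 50 "to accommodate for patients who are enrolled in the study but who are subsequently excluded because of inability to complete the monitoring session".

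**Incomplete recordings.** Section 3.1(a) sets the target as follows: "We plan to recruit up to 50 study subjects to complete the entire 60 minutes of testing". It then says: "Data from those who start the uEMG recordings but are unable to complete the full duration will still be analyzed", provided that the reason is not withdrawal of consent. The only exclusion it names is: "Those who withdraw consent will be excluded for data collection and analysis". Section 2.1, after the list of case report form items, leaves the use of a recording with missing data to the sponsor, case by case.

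**Withdrawal by the investigator.** Section 8 says: "Subjects may be withdrawn by the investigator if the clinical circumstances require immediate delivery". In that event "uEMG recording will be stopped at that time and no further data will be collected".

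**Labor status.** Section 14.2 (Contraction analysis) classes delivery within 24 hours as in labor, delivery at 72 hours or later as not in labor, and anything between as transitioning.

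**The concern.** There are two separate defects.

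First, beta conventionally denotes the type II error, so the printed value commits the study to 20% power. That does not fit the sample size beside it. Even a reader who silently corrects beta cannot tell what test 23 was meant to support, because neither the test nor its sidedness is given.

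Second, the rule for a woman whose recording starts but stops early depends on the section consulted. If the choice is left until the data are in hand, the analysis set can be chosen with the results in view. The choice matters most for labor prediction, because one foreseeable reason for stopping early, the need for immediate delivery, is tied to the outcome being predicted.

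**Working it through.** **Inputs (section 14.1).** p0 = 0.50 (minimum acceptable), p1 = 0.75 (expected), difference 0.25, alpha 0.05, N = 23. Reading these as one sample with .75 against .50 is an assumption. Variances: p0(1−p0) = 0.25 and p1(1−p1) = 0.1875. Normal quantiles: 1.645 (one-sided 0.05), 1.960 (two-sided 0.05), 0.842 (80% power), −0.842 (20% power).

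**Formula A (null and alternative variances).** n = [(z_alpha·√0.25 + z_power·√0.1875)/0.25]².

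**Formula B (unpooled variance).** n = (z_alpha + z_power)²·0.1875/0.25².

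| Power | Sides | A | B |
|---|---|---|---|
| 80% | one | 22.54 | 18.55 |
| 80% | two | 28.92 | 23.55 |
| 20% (beta = 0.8 as printed) | one | 3.36 | 1.94 |
| 20% (beta = 0.8 as printed) | two | 6.06 | 3.75 |

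*Reproducing 23.* Formula A, one-sided, 80% power: [(1.645 × 0.5 + 0.842 × 0.433)/0.25]² = 22.54, rounded up to 23. Formula B, two-sided, 80% power: (1.960 + 0.842)² × 3 = 23.55. Strictly this rounds up to 24, but 23 then has about 79% power. The two-group reading (.75 against .25) gives the same unrounded totals.

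*Beta as printed.* Rounded up, the 20% rows need 2 to 7 patients. None comes near 23.

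*Log-odds forms.* The section names odds ratios, so I also ran the one-sample log odds (odds 3 against 1, ln 3 = 1.0986) at 80% power:

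| Variance used | One-sided | Two-sided |
|---|---|---|
| Null only (1/0.25 = 4) | 20.5 | 26.0 |
| Null and alternative | 22.7 | 28.5 |
| Alternative only (1/0.1875 = 5.33) | 27.3 | 34.7 |

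The spread of 20.5 to 34.7 shows that 23 does not identify the method.

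**Exact binomial power.**
- n = 23, one-sided: reject at 16 or more; alpha 0.0466, power 0.804.
- n = 23, two-sided: upper critical value 17; alpha 2 × 0.0173 = 0.035, power 0.654.
- n = 50: power 0.971 one-sided (critical value 32), 0.945 two-sided (33).

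**The rules side by side.**

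| Woman | 3.1(a) | 14.1 |
|---|---|---|
| Enrolled, never starts recording | not addressed | can be read as excluded |
| Starts, withdraws consent | excluded | can be read as excluded |
| Starts, does not finish, consent kept | analyzed | excluded |

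Only the last row conflicts. Section 2.1 adds a third answer for it if a short recording counts as missing data. A woman withdrawn under section 8 for immediate delivery falls in this row, since she has not withdrawn consent. Assuming that she does deliver within 24 hours, section 14.2 classes her as in labor, so dropping such women removes cases from that class only.

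**The allowance.** 50 − 23 = 27, and 27/50 = 54%. Section 14.1 attributes all of it to not completing the session, and the documents give no non-completion rate. If none to all of the 27 were started but incomplete (an assumption), the choice of rule moves the evaluable number by 0 to 27. That is a bound, not an estimate.

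**The case against.** The strongest reply is that the beta entry is a slip of notation. Someone wrote the power where the type II error belongs, and nothing in the design changes. Section 14.1 calls this a pilot, and the endpoints in section 14 are mostly descriptive: mean interpretability, RMS error, percent agreement, sensitivity. This stands as to consequence: 23 and 50 are unaffected. It does not make the printed error rate right, nor supply the missing test and sidedness.

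A reader might go further and infer that 23 must come from a one-sided test, so that a two-sided analysis would be underpowered. The documents do not support that. Formula A fits 23 one-sided, but formula B gives 23.55 two-sided. The 65% figure applies only if an exact two-sided binomial test is intended.

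On the analysis set, a reader might infer that sections 3.1 and 14.1 are opposed for all non-completers. They are not. Section 14.1 speaks of enrolled patients, and section 4.1 allows consent in the office before labor, so some may never start; others may withdraw consent. Section 5 also lets recordings be stopped and restarted, which should reduce permanent non-completion. The conflict is confined to women who start, do not finish and keep consent, but for them it remains.

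Nor do the documents support bias in every endpoint. The labor class bears on labor prediction, not on heart-rate agreement. The imbalance concerns only section 8 withdrawals, a group probably reduced by the entry exclusion for fetal distress and emergent delivery. Women who have pads removed on request may fall in any class.

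**Conclusion.** Both parts hold in limited form.

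(1) The printed beta is wrong. At 20% power the section's own inputs need about 2 to 7 patients, not 23; at 80% power 23 is a plausible result. The test and sidedness are unstated and cannot be inferred. Exact power at 23 would be about 80% one-sided or 65% two-sided. This rests on reading the inputs as .75 against .50.

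(2) For started-but-incomplete recordings with consent kept, three sections give three different answers. The number affected is unknown. The direction of possible bias is clear only for women withdrawn for immediate delivery, and only in the labor-prediction analysis.

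The inference that the study is too small is not supported. The weakness lies in the stated error rate and the definition of the analysis set. It should be corrected, but it does not threaten the study.

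**What to change.** **Section 14.1, sample size.** Replace the printed beta with beta = 0.20 (power 80%). State the hypothesis, the test and the sidedness actually used. If an exact binomial test is intended, report its power at 23: about 65% two-sided or about 80% one-sided.

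**Sections 2.1, 3.1(a) and 14.1, incomplete recordings.** Reconcile them into one prespecified rule for all endpoints. The section 3.1 rule is preferable: analyze what was recorded unless consent is withdrawn. It avoids a loss tied to delivery and suits Endpoint 1.1, which is already a fraction of the time recorded. Make the sponsor's case-by-case decision in section 2.1 subject to this rule, so that it is not taken after the data are seen.

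**Section 14.1, allowance.** Restate the reason for going from 23 to 50 in terms of the losses that the chosen rule makes. Under the section 3.1 rule these are women who never start and women who withdraw consent.

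**Cost.** Wording only; 23 and the cap of 50 stay. The stated power may look less favourable if an exact two-sided test is intended. Some analyzed recordings will be shorter than 60 minutes and may hold fewer than the 10 contractions assumed per patient.
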